10.2 Secondary study parameter(s)

The efficacy of taVNS and sham stimulation in alleviating stress-related effects, such as negative affect and feelings of stress, pain, and unpleasantness, will be determined

based on scores on the I-PANAS-SF and the 0-100 Visual Analog Scales (VASs). Scores will be compared between the two groups using the same statistical approach as that for the primary outcome.

To evaluate the effect of taVNS vs. sham on autonomic parameters, such as heart rate variability and skin conductance, a mixed-effects model will also be used. This model allows for the evaluation of the impact of taVNS on each autonomic parameter while accounting for the repeated measure within subjects.

To assess the effect of taVNS vs. sham on pulse rate variability (PRV), as a measure of vagal tone of the autonomous nervous system, all photoplethysmography data files will be processed using a custom-written MATLAB script (MATLAB R2020a). Systolic peaks will be detected using the peak detection method and considered as the pulse times for calculating pulse intervals and PRV. Root mean square of successive differences (RMSSD) will be calculated first for the 6-minute baseline period and then over fixed 5-minute intervals, following standard practice. For statistical analysis, the RMSSD change from pre-intervention (baseline) will be calculated for each subject under each condition (i.e. taVNS and sham). Marginal linear mixed models (using the R lme4 function) will be used to compare RMSSD change from baseline between conditions, using R Statistical Software version 3.6.3 (2020-02-29). RMSSD (change from baseline) will be the dependent variable, with condition (taVNS versus sham) as the within-subject independent variable. Both the main effects and the two-way interaction will be included in the model. Model fit will be assessed using the Kronecker product of an unstructured and a first-order autoregressive variance-covariance matrix, based on the lowest value of Akaike's Information Criterion. The main effect of condition will test the hypothesis of a significant difference in RMSSD between conditions over the entire time course.

Furthermore, HRV data obtained from the FitBit and Shimmer3 GSR will be compared for accuracy using linear mixed-effects models.

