3. STUDY DESIGN

The proposed project concerns a monocentric, prospective, double-blind, randomized, placebo-controlled interventional trial with a (1:1) parallel design. It is anticipated to span a total duration of 2 years, encompassing recruitment, intervention, and singular measurements conducted at the NUTRIM Clinical Research Unit (CRU) at Maastricht University.

Recruitment procedures are outlined in paragraph 11.2. Interested study participants will receive a comprehensive electronic information letter and verbal explanation of the study by phone. At least 7 days later, they will be invited to attend an inclusion visit at Maastricht University. During this visit, participants will undergo eligibility screening and will receive detailed instructions about the study procedures. When eligible for inclusion, subjects will be asked to provide written informed consent to participate in the study. Following this, participants will be asked to complete several (digital) questionnaires, including the baseline questionnaire, GAD-7, PHQ-9, and the BFI. All information obtained during this screening visit, including participant data and study-related details, will be securely recorded using Castor, an electronic data capture system. After signing the informed consent form, participants will be randomized in a 1:1 parallel fashion by an investigator to receive either taVNS or sham stimulation on the second test day, with appropriate blinding procedures in place.

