10.1 Primary study parameter(s)

The efficacy of taVNS in attenuating the acute stress response induced by the validated Maastricht Acute Stress Task (MAST) among healthy subjects will be determined based on cortisol levels in saliva samples, using an intention-to-treat principle. A repeated measures ANOVA will be utilized to evaluate both intergroup differences and within-group changes in cortisol levels across the different time points. If the assumption of normality is violated, a nonparametric equivalent will be employed. Multivariable regression analysis will be performed to correct for confounding effects of age, gender, and mental health (i.e. GAD-7, PHQ-9, BFI). Differences in cortisol saliva levels, with corresponding 95% confidence intervals (CIs) and two-sided p-values, will be calculated at a type I error level of 0.05.

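### The RMSSD model compares unadjusted change from baseline between parallel arms; adding the baseline RMSSD already computed as a covariate is a nearly free gain in precision

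*Protocol*

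**What the plan says.** Section 10.2 of the protocol sets out the RMSSD analysis in some detail. RMSSD is computed for a 6-minute pre-intervention period and then for successive 5-minute intervals. Next, "the RMSSD change from pre-intervention (baseline) will be calculated for each subject", and "RMSSD (change from baseline) will be the dependent variable". On the model terms it says "Both the main effects and the two-way interaction will be included in the model". The second factor is not named but is presumably time. The tested effect is fixed as well: "The main effect of condition will test the hypothesis of a significant difference in RMSSD between conditions over the entire time course".

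Baseline RMSSD therefore enters by subtraction only. The one adjustment set in section 10 is in section 10.1, for cortisol: age, gender, GAD-7, PHQ-9 and BFI. It contains no baseline value of an outcome.

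Section 3 describes a "placebo-controlled interventional trial with a (1:1) parallel design", so the condition effect compares different people.

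**The concern.** Using a raw change score as the outcome assumes that each unit of baseline RMSSD carries forward as exactly one unit of later RMSSD. If the true regression slope is below 1, participants who start high tend to fall and those who start low tend to rise, whatever they received. A chance difference between the arms at baseline then passes, with its sign reversed, into the estimated arm effect. If the slope is above 1, the subtraction corrects too little. Either way the residual variance is larger than it need be.

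At stake is precision, and how far the result depends on the imbalance that happens to occur, for the variable that section 10.2 names as its measure of vagal tone. The sample size in section 4.4 was set for cortisol, so the protocol plans no power for RMSSD.

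**Working it through.** **Inputs from the protocol.** Parallel 1:1 design (section 3). 54 participants required and 60 recruited, that is 27 to 30 per arm (section 4.4). Two-sided alpha 0.05 (section 10.1). Recording runs from before stimulation to 60 minutes after the stress task (section 8.3.2).

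**Inputs assumed.** The baseline-to-follow-up correlation (rho) and the ratio of follow-up SD to baseline SD (s). The protocol gives neither for RMSSD.

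**The plan's own figure.** The 54 reproduces as a comparison of 85% with 50% at 80% power, two-sided, pooled variance, no continuity correction: (1.96·√(2·0.675·0.325) + 0.8416·√(0.85·0.15 + 0.50·0.50))² / 0.35² = 1.815² / 0.1225 = 26.9, so 27 per arm. It concerns cortisol and says nothing about RMSSD.

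**Chance imbalance.** The standard error of the baseline difference between arms, in baseline SDs, is √(2/27) = 0.27 or √(2/30) = 0.26.

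**How imbalance enters.** The slope of follow-up on baseline is rho·s. Given a baseline difference D, the change-score arm effect is shifted by (rho·s − 1)·D. With s = 1 and D = 0.26 SD, the shift is −0.18 SD (rho 0.3), −0.13 (0.5), −0.08 (0.7) and −0.03 (0.9).

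A simulation of 20,000 trials at 30 per arm with s = 1 gave:
- Overall rejection of a true null: about 5% for both methods.
- Rejection when the imbalance exceeds one standard error: 10.7%, 8.6%, 7.2% and 5.9% for the change score at rho 0.3, 0.5, 0.7 and 0.9, against about 5% with adjustment.
- Correlation of the arm effect with the imbalance: −0.59, −0.50, −0.39 and −0.23 for the change score, about 0 with adjustment.

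**Single interval.** In units of the baseline variance, the change score has variance s² + 1 − 2·rho·s and the adjusted outcome has s²·(1 − rho²). Power uses the noncentral t (52, then 51 degrees of freedom), scaled so that the change score has 80% at N = 54.

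| rho | s | slope | change | adjusted | cut | 80% becomes |
|---|---|---|---|---|---|---|
| 0.5 | 1.0 | 0.50 | 1.00 | 0.75 | 25% | 90% |
| 0.7 | 1.0 | 0.70 | 0.60 | 0.51 | 15% | 86% |
| 0.75 | 1.0 | 0.75 | 0.50 | 0.4375 | 12.5% | 84.9% |
| 0.8 | 1.0 | 0.80 | 0.40 | 0.36 | 10% | 84% |
| 0.7 | 1.2 | 0.84 | 0.76 | 0.734 | 3.4% | 81% |
| 0.8 | 1.2 | 0.96 | 0.52 | 0.518 | 0.3% | 80% |
| 0.7 | 1.4 | 0.98 | 1.00 | 0.9996 | about 0 | 80% |

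Allowing for estimation of the slope costs less than 1 point of power.

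**Time course.** The tested effect averages over about 21 intervals if stimulation, stress task and recovery are all included: (30 + 15 + 60)/5 = 21. Let m be the variance of that mean and c its covariance with baseline, at unit variances. The change score has m + 1 − 2c and the adjusted outcome m − c². Serial decay is represented by a persistent share plus a first-order autoregressive remainder:
- Share 0.5, autoregression 0.80: 0.481 against 0.316, a cut of 34%; 80% power becomes 93%.
- Share 0.7, autoregression 0.95: 0.158 against 0.144, a cut of 9%; 80% power becomes 84%.

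**The case against.** The strongest reply is that nothing here is an error. In a randomised comparison the change score is a legitimate estimator, unbiased on average and with the nominal type I error, and no stated RMSSD figure is wrong because the protocol states none. That stands, and it is why the point is graded minor.

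The second reply is that the gain depends on the slope and not on the correlation alone. If RMSSD varies more after baseline than at baseline, the slope can be close to 1 with a correlation well below 1, and adjustment then gains almost nothing (last two rows of the table). That also stands. Equal variance is not an obviously safe assumption when the later intervals span stimulation, an acute stressor and recovery.

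The third is that covariates may be set in a statistical analysis plan that is not shown. This carries less weight. The protocol itself fixes the outcome, the terms, the covariance candidates and the tested effect, and a later plan that followed it would carry the unadjusted change score forward.

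The fourth is that the same paragraph has a larger fault: it makes condition a within-subject variable and says that "the RMSSD change from pre-intervention (baseline) will be calculated for each subject under each condition", although each participant receives only one condition. That needs correcting, but coding condition as between-subject leaves the unadjusted change score where it is.

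**Conclusion.** The point holds as an efficiency and conditional-imbalance improvement on one secondary measure, of minor severity. With equal variances, the single-interval variance falls by 25%, 15% or 10% at rho 0.5, 0.7 or 0.8. For the time-course mean with decaying correlation it falls by about 9% to 34%, and 80% power becomes about 84% to 93%. The power gain for a single interval is already just under 5 points at rho 0.75, and it vanishes as the slope approaches 1. All of this rests on assumed correlations and SD ratios.

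A reader might infer three stronger things that the documents do not support:
- **That the RMSSD comparison is biased or invalid.** Randomisation rules this out on average; the effect is conditional on the imbalance that occurs.
- **That the gain is very large.** Assuming one common correlation of 0.5 across all 21 intervals gives a variance cut of 48% (0.524 against 0.274). Section 10.2 itself names a first-order autoregressive component, so serial decay is the more natural assumption.
- **That secondary objective 2 stands or falls on this model.** Section 2.2 also lists blood pressure, skin conductance and heart rate variability from two devices under that objective.

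The primary cortisol analysis is not affected.

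**What to change.** In section 10.2, add each participant's baseline RMSSD as a covariate to the RMSSD mixed model, with a baseline-by-time term if wanted. The other terms are arm (coded as between-subject), time and arm-by-time. Report the baseline-adjusted arm difference with its confidence interval. The outcome may remain change from baseline, because once baseline is in the model the arm effect is the same for change and for level.

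The cost is one line of text and one degree of freedom (more if baseline-by-time is included). No new data are needed: the baseline value is already computed to form the change score, so a usable baseline recording is already required for every participant.

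### Analysing vagal tone as untransformed RMSSD change, with no baseline covariate, can cost power if changes scale with the resting level; ln(RMSSD) adjusted for ln(baseline) is a cheap improvement

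*Protocol*

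**What the plan says.** Protocol section 10.2 sets out the pulse rate variability analysis in detail:

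- Windows: "Root mean square of successive differences (RMSSD) will be calculated first for the 6-minute baseline period and then over fixed 5-minute intervals".
- Derived variable: "the RMSSD change from pre-intervention (baseline) will be calculated for each subject".
- Model: "Marginal linear mixed models (using the R lme4 function) will be used to compare RMSSD change from baseline between conditions".
- Outcome: "RMSSD (change from baseline) will be the dependent variable", with condition named as a within-subject factor.
- Test: "The main effect of condition will test the hypothesis of a significant difference in RMSSD between conditions over the entire time course".

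It also gives the R version and a covariance structure (an unstructured matrix crossed with a first-order autoregressive one, by Kronecker product). It names no logarithm, ratio or baseline covariate. The fallback in section 10.1, "If the assumption of normality is violated, a nonparametric equivalent will be employed", belongs to cortisol; section 10.2 extends the primary-outcome approach only to the I-PANAS-SF and VAS scores. The switch between t-test and Mann-Whitney test in the opening of section 10 concerns two-group comparisons, not this model.

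The protocol gives no mean, SD, effect size or power for RMSSD.

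**The concern.** RMSSD is a root mean square, so it is bounded below by zero. Someone resting at 15 ms can fall by at most 15 ms; someone resting at 80 ms can fall by 80. By the protocol's own rationale (section 1.4), stress suppresses vagal activity, so the floor lies in the direction in which the MAST should push RMSSD.

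Subtracting baseline removes each person's level. It does not remove a spread of the change that grows with that level. If changes are roughly proportional, the same 25% rise is 5 ms for a person at 20 ms and 25 ms for a person at 100 ms. Participants with high resting values then supply much of the residual variation and much of the estimated effect. The planned covariance may differ between repeated measurements, but it cannot vary with a participant's resting level.

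At stake are the efficiency and the readability of the test of secondary hypothesis 2 (section 2.2), which predicts more parasympathetic activity under taVNS. The validity of that test is not at stake.

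**Working it through.** **The plan's own figure.** The only sample size is for cortisol responders, 85% against 50% (section 4.4). With a two-sided alpha of 0.05, power 0.80 and mean rate 0.675:

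n per arm = [1.96·√(2·0.675·0.325) + 0.842·√(0.85·0.15 + 0.50·0.50)]² / 0.35² = (1.298 + 0.517)² / 0.1225 ≈ 26.9, so 27 per arm and 54 in total.

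This reproduces the stated 54. It says nothing about RMSSD, but it supplies the 27 evaluable per arm used below.

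**Does the error grow with the level?** For m independent successive differences of fixed (normal) shape, the coefficient of variation of a root mean square is about 1/√(2m). Assuming m = 300 per window, this is 1/√600 = 0.041, giving an SD of about 0.61, 1.22 and 2.45 ms at true levels of 15, 30 and 60 ms. This component is proportional to level by construction. It is only one part of the total within-person variation, so it makes purely constant noise unlikely without proving full proportionality.

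**Assumptions for the power comparison** (none is in the protocol): lognormal RMSSD, within-person log-SD 0.2 at baseline and at follow-up, true effect +25% (ln 1.25 = 0.223), between-person log-SD s, 27 per arm, condition compared between subjects.

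*Log change.* SE = 0.2·√2·√(2/27) = 0.0770; 0.223/0.0770 = 2.90; power ≈ Φ(2.90 − 1.96) ≈ 0.82, whatever s is.

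*Log RMSSD adjusted for log baseline.* Residual variance = (s² + 0.04)(1 − ρ²), with ρ = s²/(s² + 0.04).
- s = 0.3: ρ = 0.692; variance 0.0677; SE 0.0708; ratio 3.15; power ≈ 0.88.
- s = 0.6: ρ = 0.90; variance 0.0760; SE 0.0750; ratio 2.97; power ≈ 0.84 (83% by simulation).

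*Raw change.* The mean effect scales with the average level, exp(s²/2), and the SD with the root mean square level, exp(s²). The signal-to-noise ratio is therefore multiplied by about exp(−s²/2).
- s = 0.3: factor 0.956; 2.90 × 0.956 = 2.77; power ≈ 0.79 (81% by simulation).
- s = 0.6: factor 0.835; 2.90 × 0.835 = 2.42; power ≈ 0.68 (69% by simulation).

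**Nearer the planned design.** A second simulation used 12 post-baseline windows per person, 27 per arm, within-person log-SD 0.2 or 0.35, and proportional effects sized for about 80% power on the log scale. A test on subject means stood in for the main effect of condition.

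| Between-person log-SD | Raw change | Raw, baseline-adjusted | Log change | Log, baseline-adjusted |
|---|---|---|---|---|
| 0.3 | 78–79% | 80–85% | 78% | 84–89% |
| 0.5 | 71–73% | 72–76% | 79% | 82–85% |
| 0.7 | 62–63% | 60–65% | 79% | 79–83% |

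At 0.3 raw and log change perform alike, so most of the gain there comes from the covariate. At 0.7 the covariate does not rescue the raw scale; the gain comes from the logarithm.

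**Weight.** In these proportional scenarios, the quarter of participants with the highest baseline supplies 44–70% of the raw residual sum of squares, against 26–35% on the log scale. With constant noise in ms it supplies 26–29% on the raw scale.

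**Other noise models.** With mixed noise, raw change has 78–86% power against 79–88% for baseline-adjusted log RMSSD (log-SD 0.3–0.6). With noise and effect both constant in ms, raw change has 78–79% against 53–72% for unadjusted log change.

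**Type I error** of the raw analysis under proportional noise: 0.043–0.053.

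**The case against.** The strongest objection is that the protocol contains none of the inputs that create the loss. Non-negativity does not imply that changes scale with level, and an age range of 18 to 65 gives no spread. A simulation in which baseline, noise and effect are all multiplicative favours the log scale by construction, and constant noise in ms turns the ranking round. This stands, and it is why the point is conditional.

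A reader might infer that high-RMSSD participants will dominate the comparison and that power is certainly lost. The documents do not support that. The loss on the raw scale is about nil when people differ little, and it becomes large only with a wide spread.

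A reader might also infer that the model imposes one common error variance. That misdescribes the plan: the Kronecker structure allows variances to differ between repeated measurements, though not with a participant's resting level.

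Section 10.2 does not say that the change is an absolute one. Sections 2.1 and 4.4 express cortisol change as a percentage. If percentage change were meant here, most of the loss would disappear (79–80% against 81–82% for log change in the proportional case). An absolute difference is the usual reading, and the text should settle it.

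Finally, transformations are often left to a statistical analysis plan. Here, however, the protocol fixes the outcome variable, model, covariance and software version, so the scale is a stated choice.

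The same sentence calls condition a within-subject factor in a parallel-group trial. That is a separate matter; the check above compares the arms between subjects.

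**Conclusion.** The point holds as an efficiency and interpretation improvement for one secondary endpoint. Under proportional noise with within-person log-SD 0.2, a +25% effect and 27 per arm, moving from raw change to baseline-adjusted log RMSSD raises power by about 7 points (81% to 88%) at a between-person log-SD of 0.3, and by about 14 points (69% to 83%) at 0.6. The gain shrinks to 1–2 points at the ends of the range under mixed noise. It reverses in the constant-millisecond scenario, which is unlikely in pure form because part of the error grows with the level by construction. All these distributions are assumptions. The planned test keeps its type I error near 5%, so nothing here makes it invalid, and neither the primary cortisol analysis nor the sample size is touched.

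**What to change.** In section 10.2, make ln(RMSSD) in each 5-minute window the dependent variable, with ln(baseline RMSSD) as a covariate. Report the effect of taVNS against sham as a ratio of geometric means with 95% CI. Keep the raw change in milliseconds as a sensitivity analysis, and state that it is an absolute difference. Settle this before unblinding, so that the scale is not chosen from the results.

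The cost is about one line of analysis code. The effect is read as a ratio instead of milliseconds, and some power is lost if variability turns out not to scale with level; the sensitivity analysis would show whether the conclusion depends on the scale.

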4.4 Sample size calculation

There are no directly comparable studies available for an accurate sample size calculation, as previous research investigating the effect of tVNS on stress used different stimuli, making comparison challenging. However, previous research on the Maastricht Acute Stress Task (MAST) indicated that 85% of participants demonstrate a noticeable and quantifiable cortisol response (i.e., cortisol increase $\geq 2.5\text{nmol/l}$ from baseline) to the acute stress task (1). Anticipating that tVNS is expected to counteract the cortisol response to the MAST by 35%, resulting in an estimated 85% cortisol increase from baseline in the sham group vs. a 50% increase from baseline in the tVNS group, a sample size of 54 participants is required to detect this difference ($b=0.8$, $\alpha=0.05$). This estimate is consistent with other somewhat similar studies on tVNS. Based on previous experience with studies involving healthy volunteers, an additional six participants (10%) will be recruited to account for potential dropouts. This approach is deemed appropriate and feasible given the short and non-invasive nature of the intervention.

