10. STATISTICAL ANALYSIS

Demographic data and patient-reported data will be registered and saved in Castor by the coordinating investigator. Database cleaning will be carried out by the study coordinator and the local research nurses, using internal consistency checks and identification of database entries outside expected ranges.

Statistical analysis will be performed using IBM SPSS, R, Python, and Excel. Subject characteristics will be presented and analysed using descriptive statistics. Continuous parameters will be presented as means and standard deviations, and assessed between the two groups (taVNS vs. sham) with a two-sample unpaired t-test (for normally distributed data) or a nonparametric Mann-Whitney U test (for non-normally distributed data). Categorical variables will be represented as frequencies and analyzed using a Chi-square test or a Fisher's exact test. A p-value < 0.05 will be considered statistically significant.

Data interpretation will involve effect size estimates as appropriate for each statistical test (e.g. Cohen's *d* for t-tests, *f* for Mann-Whitney U test) as well as estimated intervals, such as 95% confidence intervals. Thereby, conclusions will not be drawn from a singular p-value alone. No missing data are expected. Primary and secondary outcomes data will be analysed based on an intention-to-treat approach.

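### The RMSSD model pairs a marginal Kronecker/AR(1) covariance with lme4, which cannot fit it; fitted alone elsewhere, that covariance would understate the standard error of the condition test

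*Protocol*

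**What the plan says.** Section 10.2 of the protocol computes RMSSD for a 6-minute baseline and then in fixed 5-minute intervals, and expresses each interval as a change from that baseline. On the model it says:

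- Model class and software: "Marginal linear mixed models (using the R lme4 function) will be used to compare RMSSD change from baseline between conditions". The R version named is 3.6.3.
- Outcome: "RMSSD (change from baseline) will be the dependent variable".
- Covariance: "Model fit will be assessed using the Kronecker product of an unstructured and a first-order autoregressive variance-covariance matrix", with a reference to the lowest AIC. No other structure is named.
- Hypothesis test: "The main effect of condition will test the hypothesis of a significant difference in RMSSD between conditions over the entire time course". The two-way interaction is also in the model.

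No random subject effect is written into this model. The paragraph on autonomic parameters just before it does plan a mixed-effects model that accounts for repeated measures within subjects. Section 3 fixes a 1:1 parallel design, so each person has one condition only, although section 10.2 calls condition a within-subject variable.

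**The concern.** There are two defects, and both remain after condition is corrected to a between-subject factor.

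First, the covariance and the software cannot be used together. The analyst must drop one of them, and the text does not say which. A separate analysis plan could not fill this as a gap, because the protocol states both elements and they conflict.

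Second, the covariance does not suit the outcome. A Kronecker product of an unstructured and an AR(1) matrix makes sense with several conditions per person. With one condition per person the unstructured factor shrinks to a variance (at most one per arm), leaving AR(1) over windows. Every window of a person carries the error of the same baseline measurement, so the correlation between distant windows stays well above zero, whereas AR(1) drives it towards zero. The declared test concerns the average difference over the whole time course, and the variance of an average is where ignored long-lag correlation does most damage.

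What is at stake is the error rate of the test on the protocol's chosen measure of vagal tone. It could be close to 5% or several times that, depending on a choice that might be made after the data are seen.

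**Working it through.** **Inputs from the protocol.** Section 10 sets the level: "A p-value < 0.05 will be considered statistically significant". Section 10.1 specifies "two-sided p-values, will be calculated at a type I error level of 0.05" for cortisol; two-sided testing is assumed here for RMSSD too. The recording covers 30 min stimulation + 15 min MAST (5 + 10) + 60 min afterwards = 105 min, and 105/5 = 21 windows if every interval is analysed (sections 3, 8.3.2, 10.2).

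**The plan's own figure.** Section 4.4 gives 54 before dropout. Reading 85% and 50% as responder proportions, with pooled proportion 0.675:

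n per arm = [1.96·√(2·0.675·0.325) + 0.8416·√(0.85·0.15 + 0.50·0.50)]² / 0.35² = (1.298 + 0.517)² / 0.1225 = 26.9, so 27 per arm and 54 in total. Then 54/0.9 = 60. The figure reproduces, but it concerns cortisol; it serves here only to set the number of people.

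**Inputs assumed.** The protocol gives no RMSSD variance or serial correlation, and does not say how many windows are analysed. Raw window errors are taken as AR(1) with correlation φ from 0 to 0.9, with baseline error of the same variance.

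**Why AR(1) fails, by hand (φ = 0).** Write d_j = e_j − e_0, with var(e) = 1. Then var(d_j) = 2, cov(d_j, d_k) = 1, and the correlation is 0.5 at every lag.

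- True variance of a person's mean over 21 windows: 2/21 + (20/21)·1 = 1.048.
- An AR(1) fit estimates a lag-one correlation r of about 0.5. Its implied variance is (2/21)·[(1+r)/(1−r) − 2r(1−r²¹)/(21(1−r)²)] = (2/21)·(3 − 0.190) = 0.268.
- Ratio of standard errors: √(0.268/1.048) = 0.505.
- Actual two-sided error at nominal 5%: P(|Z| > 1.96·0.505) = P(|Z| > 0.991), about 32%.

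For 6 windows, the true variance is 2/6 + 5/6 = 1.167 and the AR(1) variance is (2/6)·(3 − 0.656) = 0.781. The ratio of standard errors is 0.818 and the actual error about 11%.

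**Simulation, no true effect, 21 windows, 54 people (60 in some runs).** Ranges are across independent runs.

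| φ | AR(1) only: condition main effect | Random intercept only: condition-by-time |
|---|---|---|
| 0 | 32–33% | not reported |
| 0.2 | 26–29% | 5–6% |
| 0.4 | 20–21% | 7–8% |
| 0.6 | 15% | 10–11% |
| 0.8 | 9–11% | 15% |
| 0.9 | 7–8% | not reported |

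With 6 windows, AR(1) alone gives about 5–10% (at most 12%, in a run with 60 people). If the change scores themselves truly followed AR(1), the error would be about 5%.

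**Comparators.** A t-test on each person's mean change, and a random-intercept fit, both keep the main-effect test at 3.7–6.1% in every setting, simulation noise included.

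**Software.** lmer, the lme4 fitting function, was run in version 1.1-37 under R 4.3.3, not the protocol's R 3.6.3. It has no correlation argument (supplying corAR1 gives an unused-argument error), and it stops when no random effect is specified.

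**The case against.** A reader might infer that the RMSSD test as planned has far more than 5% false positives. The documents do not support that, for four reasons.

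- **The two defects are alternatives.** Used as named, lme4 forces a random effect and rules out AR(1). With a subject intercept, the declared main-effect test is near 5%. Inflation of that test needs the analyst to leave lme4 and fit AR(1) alone. This stands.
- **The absence of a subject effect is inferred.** It comes from the word marginal and from silence. The same sentence says mixed models, and the preceding paragraph accounts for repeated measures. This stands, although neither phrase adds a subject effect to this model.
- **The AIC clause may imply a choice among structures.** If AIC chose between AR(1) and compound symmetry, the error would be 4–18%, and about 5% with independent window noise, where AR(1) alone is at its worst. This stands in part: only one structure is named, so no comparison is defined.
- **The size rests on unstated quantities.** With strong serial correlation or few windows, the inflation is small. This stands.

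It can also be said that correcting the within-subject wording would force a rewrite of the covariance sentence anyway. That is partly so, but relabelling the factor alone leaves both the lme4 conflict and the AR(1) misfit in place.

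A reader might further infer that the whole mechanistic claim depends on this standard error. Secondary objective 2 also uses blood pressure, skin conductance and HRV from two devices, and section 10 says conclusions will not rest on one p-value. The primary cortisol analysis is unaffected.

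**Conclusion.** The point holds in a conditional form. The RMSSD paragraph is internally inconsistent as written, and the covariance it names is unsuited to change scores that share one baseline. The condition test is anti-conservative if AR(1) alone is fitted: roughly 7–33% with 21 windows and about 5–10% with 6, for assumed serial correlations of 0 to 0.9 and equal-variance baseline error. Under lme4 with a random subject intercept the declared test stays near 5%. The condition-by-time test then runs at about 5–15% for φ between 0.2 and 0.8 with 21 windows, but the protocol does not name that interaction as its hypothesis test. Severity is should-fix: this is an error in stated text rather than missing detail, it affects one secondary measure, and it is cheap to correct.

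**What to change.** Replace the lme4 sentence and the Kronecker/AIC sentence in section 10.2 with one runnable model in which arm is between-subject. Either of these would do:

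1. RMSSD change with arm, window (as a factor) and arm-by-window, a random subject intercept and AR(1) residuals over windows, with small-sample degrees of freedom. For example, nlme::lme with corAR1.
2. An ANCOVA of each person's mean RMSSD over pre-specified windows, adjusted for baseline RMSSD. This needs no covariance model over time.

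In both cases, state which windows enter the analysis. The first option keeps the arm-by-window comparison; the second gives it up for simplicity. The cost is one paragraph and a few lines of code, with no extra data or participants. The interval will be somewhat wider than under AR(1) alone, but correct.
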